5 STUDY SCHEDULE

The study will begin on 1st April 2021 and end on 31st March 2024 which is the 36-month period when staff are fully funded to conduct the study. Data collection will commence once approvals are in place.

When service users recruited in clinic or via social media volunteer to take part in an interview, a member of the research team will contact them by telephone, email or encrypted online messaging service (e.g. WhatsApp) (according to preference) within a week. The researcher will determine eligibility, explain the study and arrange a convenient time for the interview.

Service users recruited online will provide information to determine eligibility using a secure online form. A member of the research team will contact them by telephone, email or encrypted online messaging service (e.g. WhatsApp) (according to preference) within a week to explain the study and arrange a convenient time for the interview. The online information will explain that not all interview volunteers will be contacted.

Service user interviews will take 60-90 minutes and service users will be interviewed only once. Healthcare staff and stakeholders will take 45-60 minutes and participants may be interviewed more than once if they consent to be re-contacted about a second interview.

Interview participants will be able to re-consider taking part in the study by cancelling the interview appointment, or any time during the interview, or within 4 weeks of the interview taking place (after which time the transcripts will be incorporated into analysis) by contacting the research team.

6 ELIGIBILITY CRITERIA

6.1 Inclusion Criteria

Sexual health service users aged 16 years and older, who have accessed online and/or clinic-based services within the past 12 months within the three case study areas.

Healthcare professionals, staff, commissioners and other stakeholders involved in implementation of OPSS services within the three case study areas.

6.2 Exclusion Criteria

Those unable to give fully informed consent or with insufficient understanding of English will not be included.

7 RECRUITMENT

The following section describes how participants will be recruited for interviews in Workstream 1.2 and Workstream 3.

Workstream 1 (Impact evaluation)

Workstream 1.2 - Service user and healthcare professional experiences and views about acceptability of OPSS and clinic-based services

Service user interviews

Three different populations of services users will be recruited:

- Users of clinic-based services (10-15 per area)
- Users of online postal self-sampling services (10-15 per area)
- Service users who have used both (10-15 per area)

Users of clinic-based services will be identified and recruited by a member of the healthcare team on the day of their consultation (which may be conducted face-to-face, by telephone or by video). Targeted responsive recruitment of specific patient profiles within clinics will include understanding and tailoring recruitment processes to local inter-disciplinary teams, providing regular feedback on relative recruitment success, and iteratively developing responsive action plans. Where research nurses or clinical trial practitioners are available, they are likely to support patient identification and recruitment, however elsewhere reception, nursing or medical staff may assist in this process. The first name and preferred contact details for each service user identified will be emailed to the research team at UCL using nhs.net email accounts.

Users of online postal self-sampling services only will be recruited via (i) information posted on the OPSS website with a link taking them to an online form (held securely within the UCL Data Safe Haven) where they will be asked to complete their contact details and screening information; and (ii) advertisements using social media and the study website, and local community settings (*Appendix* 6). They will email the research team at UCL with their first name and preferred contact information.

Service users who have accessed both types of service will be recruited using all of the methods described above.

When a member of the research team contacts service users recruited in clinic or via social media to explain the study, they will check eligibility using a short screening questionnaire (*Appendix 7*) in order to fulfil the sampling criteria according to age, gender, ethnicity, sexuality and OPSS service usage. Service users recruited via an OPSS website will provide information relating to eligibility and the sampling criteria when they submit their contact details. A member of the research team will contact those who are eligible and fulfil the sampling criteria to explain the study.

Interviews will be conducted at a mutually convenient time either F2F on clinic or university premises or via phone, or online meeting (e.g. Microsoft Teams, Skype) according to participant preference. It is expected that most interviews will take 60-90 minutes. All interviews throughout the programme will be digitally recorded, transcribed verbatim by professional services, and fully anonymised. Participants will be reimbursed £30/ interview.

Healthcare professional interviews

Healthcare professional interviews (10-15 per area) exploring experiences and views about acceptability of OPSS and clinic-based services will also be responsive to findings from earlier parts of the study. If initial data suggest that healthcare professionals may not wish to provide OPSS because using it is complicated and time-consuming, then data will be deliberately sought to explore and test this. It is anticipated that the interviews will also explore what influences their preference to providing testing through online services (or not) and/or clinic-based services, whether their opinions and experiences were sought and or addressed and if/how they could be improved. These interviews link with those in Workstream 3.2 (as below).

Workstream 3 (Implementation evaluation)

Participants for Workstream 3 will be recruited purposively to ensure a balance of perspectives from across the two study areas from a range of different stakeholders (as detailed below), according to their availability and willingness to take part. Participants may take part in more than one interview if they consent to do so.

Workstream 3.1: Contextual drivers

Key informant/stakeholder interviews (5-10 per area) with people involved in setting up and implementing OPSS.

Workstream 3.2: Planned and actual implementation processes

Semi-structured interviews with NHS Board members/commissioners (*6 across all areas*), the tendering team (*8-10 across all areas*), clinical leads, service managers and clinical healthcare professionals who came together to decide how to deliver OPSS (*10-12 across all areas*).

Contextual observation with a range of already identified members of NHS staff (*max 3-5 per area* which are likely to include a member of the administrative staff, a health adviser and a nurse/clinician) who will be approached by a member of the research team via email.

8 CONSENT

Service users

Users of clinic-based services will be identified and recruited by a member of the healthcare team on the day of their consultation (which may be conducted face-to-face, by telephone or by video). The healthcare team will provide an information leaflet (*Appendix 8*) and explain that participation in the interview is voluntary and will take about 60-90 minutes. *Users of online postal self-sampling services* will be recruited either (i) by a member the healthcare team if they have a face-to-face, telephone or video consultation, or (ii) will approach the research team directly having seen online information about the study (*Appendix 6*).

A member of the research team will then contact the service user, explain the study and what taking part involves, and assess capacity to provide informed consent. They will check eligibility according to the sampling criteria using a short screening questionnaire (*Appendix 7*) for those who have not already provided this information. The member of the research team will send the Participant Information Sheet containing full details of the study by email or post, or via link to the study website (as preferred), and arrange a convenient time for the interview to take place. All participants will be able to ask questions about the research before agreeing to take part. Before the interview, participants will be able to change their mind about taking part and cancel the interview appointment.

The researcher will obtain written informed eConsent using REDcap, or verbal informed consent (as preferred among those interviewed by telephone or video) before commencing the interview. REDCap is a secure web client which will be run from within the UCL Data Safe Haven. Service users will be told that they can withdraw at any time during the interview and that, if they decide to leave the study, any information already collected will be retained and used for the purpose of the study but no additional data will be collected. At the end of the interview, they will be asked to confirm if they are still happy for their data to be included in the study.

Participation will depend on the ability to understand English sufficiently to be able to provide informed consent and answer the questions. Due to the sensitive nature of the topic, it is not appropriate for a translator to be present with the researcher and participant. It is anticipated that only a very small proportion of those approached to participate in the research will be unable to understand English sufficiently.

Healthcare staff and stakeholders

Healthcare staff and stakeholders will be invited to take part in key informant interviews. The Participant Information Sheet containing full details of the study will be emailed to them. If they are interested in taking part, a member of the research team will contact them and arrange a convenient time for the interview to take place. They will be able to ask questions about the research before agreeing to take part. The researcher will obtain written informed eConsent using REDcap, or verbal informed consent (as preferred among those interviewed by telephone or video) before commencing the interview. Healthcare staff and stakeholders may be interviewed more than once and the option to re-contacted about a second interview will be included in the consent form.

Contextual observation

NHS staff will be invited to take part in a contextual observational interview and the Participant Information Sheet will be emailed to them. If they are interested in participating, a mutually convenient day will be determined. It will be emphasised participation/non-participation will not affect their employment with the participating clinic in any way. After determining that they fully understand the nature of the research, informed consent will be obtained using REDcap, as described above.

A member of the clinical care team will inform service users on the day of their consultation if the healthcare professional they are to see is participating in planned contextual observations. They will explain the study observations to potential participants, and provide a Participant Information Sheet in advance of their clinic appointment. A member of the clinical care team will go through the consent procedures, answer any questions they may have about the study, and will complete the consent process with them prior to the scheduled appointment. If the service user does not want their consultation observed then the researcher will not observe the consultation even if the healthcare professional has provided consent.

When contextual observation involves observing work processes managing clinical records and/or administrative tasks, the observer will either position themselves so as not to be able to see the clinical records or ask staff to use 'dummy records' to demonstrate processes.

Observation of information in the clinic about online services will not involve observing or taking notes on any interactions between staff or service users. The researcher will not seek to observe patient identifiable data.

9 DATA ANALYSIS

Workstream 1 (Impact evaluation)

Workstream 1.1 - Measurement of impact of OPSS on health inequalities, access, clinical and public health outcomes

For each case study area and primary outcome separately:

- Change will be analysed after introduction of OPSS in the overall number of tests and the proportion of those testing with particular population characteristics
- Change will be expressed in the rate of testing per year and, informally using estimates of the catchment area population size, change in the rate of testing per 1000 population per month, using Poisson regression and adjusting for population characteristics to address any possible confounding
- Change will be formally assessed in health inequality by testing for differential change over time (pre and post OPSS) by population characteristic (e.g. gender, ethnic minority group) through including interaction terms in the regression models
- Data will be pooled across the three areas to test for different change between areas

Analyses of Natsal-3 and Natsal-4 will provide estimates of the change over time in key outcomes within the general population, and insight into whether change is greater in areas that fully implemented OPSS services than others.

Our initial analysis is expected to be robust to confounding due to population change. To further address the possibility of confounding arising from other service changes that may have occurred at a similar time to OPSS, and the immediate impact of the COVID-19 pandemic, an analysis will be conducted based on an in-depth understanding of the health service provision over the full range of

time 2015-2022 in our case study areas. By collecting the dates of other changes in provision and pre-specifying the likely lag for these changes to affect our outcomes, Poisson regression models can be developed for our outcomes in continuous time that permit an 'interrupted time series' analysis to attempt to address the specific effect of OPSS adjusting for the effects of other changes.

Workstream 1.2 - Service user and healthcare professional experiences and views about acceptability of OPSS and clinic-based services

- 1. Quantitative data: The uptake of each component of the intervention will be analysed using logistic regression modelling for each component, stratifying by age, gender, sexuality, ethnicity, and IMD.
- 2. Qualitative data: All qualitative data collected in Workstreams 1 and 3 will be analysed using a realist logic of analysis aimed at developing iterative refinements of the initial programme theory to include contexts (C), mechanisms (M) and outcomes (O) configurations (CMOCs). Some of these CMOCs will likely relate to the four constructs of NPT (coherence, cognitive participation, collective action and reflexive monitoring) at the three stages of normalisation (initiation, embedding and integration) as this is our candidate theory for analysing the implementation process. Other CMOCs will relate to the constructs found within the different relevant formal theories that will be used to explain those parts of the programme theory that cannot be accounted for by NPT alone.

The topic guides for the semi-structured interviews will therefore be theory informed and developed by the project team including those with direct of experience of working in or using sexual health services. All qualitative data will be transcribed verbatim by professional services, fully anonymised and entered into NVivo to facilitate analysis.

The planned analysis will be multi-staged. Stage 1 will use inductive thematic analysis to identify emergent themes around the characteristics of the users, provider, decision making and the OPSS journey. Data will also be analysed deductively into themes based on concepts from formal theories. Stage 2 will use a realist logic analysis to build CMOCs from the data within and across the themes generated. In this stage, data will also be sought from within and across the themes to inform our interpretations of where the CMOCs developed fit within our initial programme theory - thus gradually refining it.

Where possible and relevant, observed variation in quantitative outcomes as collected in Workstream 1 (e.g. in uptake, use, clinical and economic outcomes, and impact on health inequalities) will be used as well to develop and refine CMOCs.

Workstream 2 (Economic evaluation)

An economic evaluation will be undertaken to compare the costs and benefits for screening asymptomatic individuals undertaken using self-sampling kits ordered online, compared with screening of the same group in a clinic setting, across the case study areas. As a secondary analysis, the potential impacts on health equity associated with different types of service provision will be assessed (56).

The economic evaluation will be conducted and reported in accordance with relevant guidelines (51,52). Initially a cost-consequence analysis will be presented which involves reporting all costs and outcomes in a disaggregated manner (51). An incremental economic analysis will be conducted using the primary outcome of cost per positive case identified and the secondary outcomes of cost per patient screened, cost per patient treated and cost per partner identified / treated (if data quality on partner notification permit this). The economic component will explore how different service configurations can be used to achieve the optimal level of health benefit, within existing resource constraints. This element will identify and model patient pathways across the case study areas, assess comparative costs and outcomes, and analyse different scenarios for service configuration.

As a secondary analysis, impacts on equity will be analysed. Currently these methods are being refined and a range of possible methods will need to be considered (56). For example, recommended approaches include equity impact analysis (analyses distributional impacts on different groups) and equity trade-off analysis (examining trade-offs between improving total health and reducing health inequality) (53). Variations of multicriteria decision analysis have also been proposed as possible methods (54). As such methods have not previously been used in a sexual health context, a review of the literature will be conducted to assess the most appropriate approach and be informed by emerging practice (e.g. (57,58)). This approach will then be applied as a secondary analysis to allow decision-makers to access both a traditional analysis and a fuller analysis taking into account equity considerations.

Deterministic and probabilistic sensitivity analyses will be conducted to explore the effects of the uncertainty in the parameter estimates on the results (59). Deterministic sensitivity analysis involves varying one or more parameters while keeping the others at their baseline value. A probabilistic sensitive analysis involves varying all parameters simultaneously, and multiple sets of parameter values are sampled from defined probability distributions (60).

Workstream 3 (Implementation evaluation)

The data from Workstreams 3.1, and 3.2 will be analysed as a whole, using a realist logic of analysis to refine the initial programme theory as described above (Workstream 1.2, p22). The refined programme theory will include actions required and adaptations made to both the OPSS service, and the implementation programme. Where possible and relevant, observed variation in quantitative outcomes as collected in Workstream 1 (e.g. in uptake, use, clinical and economic outcomes, and impact on health inequalities) will be used to develop and refine our context mechanism and outcome configurations.

Workstream 4 (Development of programme theories)

Within the analytic process, interpretive cross-case comparison will be used to understand and explain how and why observed outcomes have occurred, for example, by comparing how outcomes may differ according to population group or service model, to understand how context, problem or diversity have influenced findings. Where appropriate, the following forms of reasoning will be used to make sense of the data:

- Juxtaposition of data: for example, where data about uptake of OPSS in one source enables insights into data about uptake in another source.
- Reconciling of data: where data differ in apparently similar circumstances, further investigation is appropriate in order to find explanations for why these differences have occurred.
- Adjudication of data: on the basis of whether threats to the validity of data in one source might make us question their trustworthiness compared to data from another source.
- Consolidation of data: where outcomes differ in particular contexts, an explanation can be constructed of how and why these outcomes occur differently.

The evaluation will move iteratively between the analysis of particular examples, refinement of programme theory, and further data collection to test particular parts of our programme theories. This will allow us to say 'what works, for whom and under what circumstances' for the impacts and in implementing and sustaining OPSS services.

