- Partner notification rates for those diagnosed with chlamydia, gonorrhoea and HIV

For each of these outcomes, our analysis will explore whether change differs between the areas during the time-period being analysed, and whether change in clinical outcomes differ by population characteristics (including age, gender, ethnicity, sexuality and IMD).

Workstream 1.1 – Sample size

Three contrasting settings have been selected to serve as case studies. Our key objective which is most 'demanding' of the data, and hence drives the power calculation, is the detection of differences in the change in the primary outcomes after introduction of OPSS by key population characteristics. Data will be obtained over a continuous period before, during and after implementation of OPSS. However, to simplify the power calculation (and to be conservative) the comparison of one-year periods before and after OPSS are considered (different for each area).

As an example, analysis of data from one area is considered - Birmingham, and the testing rate for STIs excluding chlamydia for which data are publicly available. The rate changed from 193 per 1000 population in 2014 (pre OPSS) to 198 per 1000 in 2016 (post OPSS). With around 140,000 tests per year there is more than 99% power to detect a change as small as 1% in the proportion of those testing with a particular characteristic (e.g. ethnic minority group or gender) whatever the proportion before OPSS.

Workstream 1.1 – Data collection

Routinely collected data is captured by existing surveillance systems in England (e.g. Chlamydia Testing Activity Dataset, GUMCAD STI surveillance, HIV self-sampling dataset).

Data on clinical outcomes will be collected from routine information held by service providers in the case study areas. In each area, service user information is collected on electronic patient record systems and website databases. For each area, work will be undertaken to specify the fields to be included in the data extraction from service user records and website databases.

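### With population size used only informally, the period-by-characteristic interaction tracks who is testing rather than subgroup testing rates, and the claim of robustness to population change has no stated support

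*Protocol*

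**What the plan says.** Protocol section 9, Workstream 1.1, sets out the following for each area and primary outcome.

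- The quantities analysed are the number of tests and the make-up of the people tested.
- A monthly rate per 1,000 residents is added "informally using estimates of the catchment area population size", and the model is described as "using Poisson regression and adjusting for population characteristics to address any possible confounding".
- Inequality is assessed formally by "testing for differential change over time (pre and post OPSS) by population characteristic", using interaction terms in the same regression models.
- The section then states: "Our initial analysis is expected to be robust to confounding due to population change".

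Section 4 (Workstream 1.1, Outcome measures) interprets differential change by age, gender, ethnicity, sexuality or deprivation as a shift in health inequality. The Sample size paragraph makes this the objective that drives power, and works it out on the share of testers: "With around 140,000 tests per year there is more than 99% power to detect a change as small as 1% in the proportion". Its example for Birmingham reads "The rate changed from 193 per 1000 population in 2014 (pre OPSS) to 198 per 1000 in 2016 (post OPSS").

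No population denominator by age, gender, ethnicity, sexuality or deprivation is named for these models.

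**The concern.** A subgroup's share of tests can rise because its members test more often, or because there are more of them. Only the first is a change in access. Counts of tests, with a denominator that is informal and describes the catchment as a whole, cannot separate the two.

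The protocol treats the interaction as its formal evidence on inequality and says that population change is not a threat to the first analysis. If subgroup populations grew at different speeds between the two periods, the stated analysis could show a change in inequality where testing rates did not move. It could also hide a real one. The areas are large, diverse cities and the data run from 2015 to 2022, so the assumption of equal subgroup growth needs support.

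**Working it through.** **Inputs from the protocol.** About 140,000 tests a year, and rates of 193 and 198 per 1,000 (section 4, Workstream 1.1, Sample size).

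**Assumptions, because the protocol gives no figures.** Two-sided 0.05; a subgroup supplying 40% of tests; Poisson variation without overdispersion; illustrative subgroup rates and populations.

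**1. The plan's own power figure.** For a change from p to p + 0.01 with 140,000 tests in each year, z = 0.01 / sqrt[p(1−p)/140,000 + (p+0.01)(0.99−p)/140,000]. The lowest value is near p = 0.5, where z = 5.29 and power is 99.96%. The stated figure reproduces for an absolute one-point change. It is power to detect a change in tester mix, whatever the cause.

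**2. Adjustment and the period ratio.** Write the expected count in period t and stratum s as N_t · exp(a + b·t + c_s), where N_t is 1 or the catchment total. The likelihood equations force fitted period totals to equal observed totals. The sum of exp(c_s) is the same in both periods and cancels, so exp(b) = (Y_1/N_1)/(Y_0/N_0), which is the crude ratio, whatever characteristics are added. Only an offset that varies by stratum and period breaks this.

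Check with constant rates of 0.20 and 0.12 and populations moving from 400,000 to 440,000 and from 600,000 to 590,000:

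- Tests: 80,000 + 72,000 = 152,000 before; 88,000 + 70,800 = 158,800 after.
- No offset: crude and adjusted ratios are both 158,800/152,000 = 1.0447.
- Catchment offset: both are 1.0447/(1,030,000/1,000,000) = 1.0143.
- Subgroup offsets: 1.000.

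This example shows the mechanism, not a likely size: its growth gap is about 12% (1.10/0.983 = 1.119). With equal rates the catchment-offset ratio is exactly 1.000. With rates of 0.20 and 0.12 and only the 400,000 group growing, by 2%, it is (153,600/152,000)/(1,008,000/1,000,000) = 1.0025, small beside 198/193 = 1.026.

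**3. The interaction.** With subgroup populations n and rates R, each count is nR, so

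interaction ratio = (ratio of the two rate ratios) × (ratio of the two population growth factors).

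A catchment-total offset cancels. In the example above the result is 1.119, although no rate changed; with subgroup offsets it is 1.000.

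**4. How often drift alone would be flagged.** The subgroup supplies 56,000 of the 140,000 tests, its population grows by g while the rest stays constant, and no rate changes:

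z = ln(1+g) / sqrt[1/56,000 + 1/84,000 + 1/(56,000(1+g)) + 1/84,000].

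| Growth gap g | ln(1+g) | Standard error | z | Flagged at two-sided 0.05 |
|---|---|---|---|---|
| 0.5% | 0.00499 | 0.00771 | 0.65 | 10% |
| 1% | 0.00995 | 0.00770 | 1.29 | 25% |
| 2% | 0.01980 | 0.00769 | 2.57 | 73% |
| 5% | 0.04879 | 0.00766 | 6.37 | about 100% |

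**5. Masking.** If the subgroup's population share moves from 40% to 41%, the growth factor ratio is (41/40)/(59/60) = 1.042. A true relative fall in its testing rate to 1/1.042 = 0.959 of its former level, compared with the rest, then gives an interaction of exactly 1.000.

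**The case against.** The strongest reply is that the protocol does not write out the model. It does not fix the data layout, the offset or its granularity, or say whether the characteristics belong to individual testers or to the area population. Subgroup offsets, or population composition entered as a time-varying covariate, would remove the identity in step 2. Such detail often belongs in a statistical analysis plan, and section 4 places the national datasets in a supplementary protocol; neither is shown.

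This stands as a limit. A reader might infer that adjustment certainly does nothing and that the robustness sentence is proven false. The documents do not support that, because both conclusions rest on the natural but unstated reading. The point survives because this protocol itself makes the denominator informal and itself asserts robustness.

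Three further replies have partial force.

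- **Size.** No subgroup growth is documented. At gaps of 0.5% or 1% a false flag is the exception, and a 2% gap yields a ratio of only 1.02. High rejection rates mainly reflect the number of tests. The power example spans about two years, which limits drift there.
- **Interrupted time series.** A time trend could absorb some gradual drift. As described, though, this analysis targets other service changes and COVID-19, and no group-specific trends are mentioned.
- **Natsal.** It gives general-population context but is not described as a denominator for these models.

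**Conclusion.** The point holds in a limited form. As section 9 reads, the formal inequality test compares tester mix between periods, and nothing stated in the protocol makes it robust to differential population growth. Under the assumptions listed, the probability of a false signal runs from about 10% at a 0.5% growth gap to about 100% at 5%, and an offsetting change in access can be hidden. With overdispersion properly allowed for, these probabilities would be lower.

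Two stronger inferences should be avoided. The first is that the overall testing rate is badly biased: with a catchment offset the bias is zero when subgroup rates are equal and 0.25% in the 2% illustration. The second is that the inequality results will be wrong: that depends on actual subgroup growth, which the protocol does not report. The power statement is arithmetically sound, but it concerns the share of testers and not subgroup rates.

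**What to change.** In section 9, Workstream 1.1:

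- Make subgroup-specific, period-specific population estimates the formal offset for the characteristics where such estimates exist: age, gender, deprivation group (derived from LSOA) and ethnicity. For ethnicity, add a sensitivity analysis for denominator error.
- Where no denominator exists, for example for sexuality, report the interaction as a change in tester mix and do not call it a change in health inequality.
- Remove the robustness sentence, or limit it to the analyses that use subgroup denominators.

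The dataset fields in Appendix 3 already include age, gender, ethnicity and LSOA, so data collection need not change. The cost is revised wording, obtaining matching population tables, and some estimation error in the denominators, mainly for ethnicity. Whether suitable tables exist for every area and period cannot be confirmed from the protocol and should be checked first.
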